1.1 Study objectives

The goal of this trial is to investigate the effect of the implementation of the KDIGO bundle¹ in patients at high risk for AKI after major surgery compared to standard of care in the same patient population. This biomarker-guided approach (individualized therapy) enables to treat patients at high risk for AKI prior to a functional damage of the kidneys.

1.2 General study design and plan

International, multicenter, two arm, randomized, controlled, parallel-group clinical trial with masked participants and outcomes assessors

2 Analysis populations

2.1 Full analysis set

The full analysis population contains all patients who were randomized.

2.2 Per protocol population

The per protocol population contains all patients without major protocol deviations. Major protocol deviations that lead to exclusion from the per protocol population are

1. violation of inclusion/exclusion criteria
2. noncompliance to the randomized intervention

2.3 Safety population

The full analysis population contains all patients who were randomized.

¹ Bundle recommended by the "Kidney Disease: Improving Global Outcomes Group" (KDIGO bundle) for at least 12 hours:

1. discontinuation of all nephrotoxic drugs when possible
2. optimization of volume status and hemodynamic parameters (consideration of a functional hemodynamic monitoring)
3. close monitoring of serum creatinine, fluid balance and urinary output
4. avoidance of hyperglycemia
5. considerations of alternatives to radiocontrast agents
6. discontinuation of angiotensin converting enzyme inhibitors and angiotensin receptor blockers in the perioperative period
7. avoidance of HES, gelatin, and chlorid-rich solutions

3 Endpoints

3.1 Primary endpoint

Occurrence of moderate or severe AKI within 72 hours after start of the intervention

3.2 Secondary endpoints

1. Adherence to the KDIGO bundle
2. Occurrence and severity of any stage of acute kidney injury within 3 days after surgery
3. Change in biomarker values during 12 hours after initial measurement of [TIMP2]*[IGFBP7]
4. Free-days of mechanical organ support through to day 3
5. Free-days of vasopressors through day 3
6. Need of RRT at day 30 and 90
7. Duration of RRT at day 30 and 90
8. Renal recovery at day 90
9. 30-day and 90-day mortality
10. ICU length-of-stay and Hospital length-of-stay
11. Major adverse kidney events (MAKE90) (defined as the composite of death, use of RRT and persistent renal dysfunction (defined as serum creatinine $\geq 2x$ to baseline value at hospital discharge)) at day 90

4 Statistical Analyses

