5.2 Descriptive summary of study data

All continuous variables will be summarized using the following descriptive statistics: n (non-missing sample size), number of missing values, mean, standard deviation, median, first and third quartile, minimum, maximum.

For categorical variables the frequency and percentages of observed levels will be reported based on the non-missing sample size. All summary tables will be structured with a column for each treatment and will be annotated with the total population size relevant to that table/treatment, including any missing observations.

Censored variables will be summarized using Kaplan Meier estimation.

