5.4 Secondary statistical analyses

Secondary outcomes will be evaluated in the full analysis set according to ITT. Secondary statistical analyses are intended to be exploratory (hypothesis generating) and will be interpreted accordingly. A two-sided p-value of ≤ 0.05 will be considered as noticeable (“significant”) without adjustment for multiplicity.

Statistical analysis of the pre-specified secondary endpoints will be performed with descriptive and inferential statistical methods. In inferential statistical analyses two-sided significance tests will be applied with a local significance level $\alpha=0.05$. All point estimates of parameters of interest will be supplemented by 95% confidence intervals unless otherwise stated.

Secondary outcomes will be evaluated and compared between the randomized treatment arms with stratification by center using the following methods. In case of normally or non-normally distributed metric outcomes, a two-way ANOVA or the van Elteren test will be applied, respectively. Categorical outcomes will be analyzed using (generalized) Cochrane Mantel Haenszel tests. Survival data will be analysed using the Kaplan-Meier method and the stratified log-rank test. Hazard ratios will be estimated based on stratified Cox proportional hazards models after checking the proportional hazards assumption based on the Schoenfeld residuals.

The duration of RRT will be evaluated in two ways.

1. If a patient dies or reaches his/her end of follow-up, the duration of RRT is finished.
2. In a competing risk analysis, besides the event of interest end of RRT, death (while RRT otherwise would be ongoing) is considered a competing event. If a patient reaches his/her end of follow-up, the duration of RRT is censored.

The duration of hospital stay will be evaluated in two ways.

1. If a patient dies or reaches his/her end of follow-up, the hospital stay is finished.
2. In a competing risk analysis, besides the event of interest end of hospital stay, death (while hospital stay otherwise would be ongoing) is considered a competing event. If a patient reaches his/her end of follow-up, the duration of hospital stay is censored.

The duration of ICU stay will be evaluated in two ways.

1. If a patient dies or reaches his/her end of follow-up, the ICU stay is finished.

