5.7 Operating characteristics

The operating characteristics of the applied design and sample size adaptation are shown below, including the total numbers of patients, percent stops after stage 1, and overall power. The operating characteristics were determined with the R software (RPACT package) in 1000000 simulation runs. Simulated data were generated assuming equal primary endpoint rates across all strata under standard care ($AKI_0=20\%$ in all strata), as well as under the interventional treatment ($AKI_1=10\%/14\%/15\%$ in all strata). The statistical analysis of simulated data was performed with Pearson's chi-squared tests.

Expected primary endpoint rate under standard care AKI_0	20%	20%	20%	20%
Expected primary endpoint rate under the interventional treatment AKI_1	10%	14%	15%	20%
Total number of patients:				
1. Minimum	618	618	618	618
2. Average	772.8	1145.1	1222.8	1400.8
3. Maximum	1418	1418	1418	1418
Percent stops after stage 1	70.8%	16.3%	9.1%	0.3%
Overall power (rejection of H_{0a})	99.9%	82.1%	66.0%	2.5%

6 Treatment of missing values

Missing values that may arise in effectiveness or safety parameters will not be replaced by any kind of statistical imputation.

7 Software

Statistical analyses will be performed using the statistical software SAS.

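### The competing-risk analysis of RRT duration in SAP 5.4 can include only patients who started RRT, so it is not the full-analysis-set ITT comparison that 5.4 claims, and it can be biased in either direction

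*SAP*

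**What the plan says.** SAP 3.2 lists "Duration of RRT at day 30 and 90" (item 7) and "Renal recovery at day 90" (item 8) without a denominator, and gives no value for patients who never had RRT or AKI. SAP 5.4 sets the population for all secondary endpoints: "Secondary outcomes will be evaluated in the full analysis set according to ITT". It plans between-arm comparisons stratified by center, and a two-sided p-value of 0.05 or less counts as noticeable.

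RRT duration is analysed in two ways in 5.4. In method 1, "If a patient dies or reaches his/her end of follow-up, the duration of RRT is finished". In method 2, "besides the event of interest end of RRT, death (while RRT otherwise would be ongoing) is considered a competing event", and patients who reach the end of follow-up are censored.

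Two general rules bear on patients without a value. Under 5.2, "the frequency and percentages of observed levels will be reported based on the non-missing sample size". Under section 6, "Missing values that may arise in effectiveness or safety parameters will not be replaced by any kind of statistical imputation".

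**The concern.** The trial aims at prevention. Its primary endpoint is "Occurrence of moderate or severe AKI within 72 hours after start of the intervention", and a bundle that prevents AKI may also change who needs RRT. An analysis that starts from RRT initiation then compares two groups that randomization did not create. If the bundle keeps some patients off RRT, the starters in the bundle arm are a different mix from those under standard care, and a difference in time to end of RRT may reflect only that mix.

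The result would nevertheless be reported under an ITT label, with a p-value. A misleading finding on RRT duration, for or against the bundle, could be read as a randomized effect.

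Method 1 has a separate weakness. Because death closes the duration, an early death on RRT scores as a short course, which looks favourable.

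**Working it through.** **1. Who can enter each analysis**

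- *Method 2.* The event is the end of RRT. The competing event is death at a time when RRT would otherwise continue. A patient who never started RRT can have neither and has no time at risk. The analysed group is the RRT starters, which contradicts the full-analysis-set statement in the same section.
- *Method 1.* The SAP does not say whether never-RRT patients enter. They could be given 0 days, which would keep all randomized patients.
- *Renal recovery.* The SAP states neither a definition nor a denominator.

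**2. The plan's own figures**

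The SAP gives no figure for RRT duration or renal recovery. Its design figures reproduce: with bounds 2.963 and 1.969, 618 per arm and rates of 20% and 14%, power is 0.800 (pooled variance) to 0.803 (unpooled), against 0.8010 stated. I use 20%, 14% and 618 per arm (the unadapted size) below.

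**3. RRT duration among starters (illustration)**

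Assumptions, none of them from the SAP: RRT starts in r0 = 5% under standard care and r1 = 3.5% with the bundle (the ratio 0.7 equals 14/20). Patients who start RRT in either arm have mean duration D. Those who start only under standard care would have mean duration d. The bundle does not alter the length of any course, and deaths are ignored.

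- Mean among starters, standard care: [r1 × D + (r0 − r1) × d] / r0
- Mean among starters, bundle: D
- Mean over all randomized, 0 days if no RRT: mean among starters × RRT rate

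For D = 14 and d = 4: (3.5 × 14 + 1.5 × 4)/5 = 55/5 = 11.0 days against 14.0. Over all randomized: 0.05 × 11.0 = 0.55 against 0.035 × 14 = 0.49.

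| D | d | Starters: standard | Starters: bundle | All randomized: standard | All randomized: bundle |
|---|---|---|---|---|---|
| 14 | 14 | 14.0 | 14.0 | 0.70 | 0.49 |
| 14 | 8 | 12.2 | 14.0 | 0.61 | 0.49 |
| 14 | 4 | 11.0 | 14.0 | 0.55 | 0.49 |
| 4 | 14 | 7.0 | 4.0 | 0.35 | 0.14 |

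Last row: (3.5 × 4 + 1.5 × 14)/5 = 35/5 = 7.0. With rates of 8% and 5.6% the starter means are unchanged, because the ratio is the same; for D = 14 and d = 4 the all-randomized means are 0.88 and 0.78.

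Among starters the bundle looks 3 days worse, neutral, or 3 days better, depending only on which courses were avoided. Over all randomized patients it is never worse.

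**4. Death in method 1**

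A patient who dies after 4 days on RRT scores 4. A survivor who comes off RRT after 14 days scores 14. If shorter is better, the death ranks ahead. Giving never-RRT patients 0 days does not cure this: a patient who dies without RRT then also scores 0, the best value.

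**5. Renal recovery, only if assessed among stage 2 or 3 AKI patients**

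Expected AKI patients: 618 × 0.20 ≈ 124 and 618 × 0.14 ≈ 87. Let the 14% who get AKI in either arm recover at rate a, and the prevented 6% at rate b (both assumed). Recovery among AKI patients is (0.14a + 0.06b)/0.20 under standard care and a with the bundle.

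- a = 50%, b = 90%: (0.070 + 0.054)/0.20 = 62% against 50%. In 200,000 simulated trials, a nominally significant result against the bundle occurs in 40.9%.
- a = b = 50%: 50% in both arms; 2.5%, the nominal rate.
- a = 70%, b = 50%: (0.098 + 0.030)/0.20 = 64% against 70%. A nominally significant result in favour of the bundle occurs in 14.3%.

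Non-recovered AKI as a share of all randomized is 7.6% against 7.0% in the first case, 10.0% against 7.0% in the second and 7.2% against 4.2% in the third.

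**The case against.** The strongest reply is that the SAP nowhere restricts these endpoints to affected patients. Section 5.4 specifies the full analysis set, and 4.8 lists RRT days and renal recovery under its intention-to-treat heading. A patient who never had RRT has a known duration of 0 days. A known zero is not a missing value, so the rules in 5.2 and section 6 do not by themselves remove that patient. The definition of renal recovery may stand in the protocol, which is not shown. Method 2 already separates death from the end of RRT. All secondary analyses are exploratory, and need of RRT, mortality and MAKE90 cover every randomized patient.

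Most of this stands. A reader might infer that both endpoints exist only in patients with AKI or RRT, and that an effective bundle will therefore look harmful. The documents do not support that. For renal recovery and method 1 the restriction is not stated. The direction depends on which cases are prevented, and the SAP is silent on that. The 20% and 14% are also stage 2 or 3 rates; if recovery were assessed in AKI of any stage, the calculation in step 5 would not apply as it is.

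The reply does not reach method 2. That analysis separates death but keeps the selected population. One could code never-RRT patients as ending RRT at time zero, but 5.4 gives no such rule, and a patient who never started has no course to end. The exploratory label deals with multiplicity and leaves selection untouched. The all-randomized endpoints help a reader to spot a misleading result, but do not make the conditional test a randomized one.

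**Conclusion.** The point holds for the competing-risk analysis of RRT duration. As written it compares RRT starters, a group formed after randomization that the bundle may change, while 5.4 presents it as a full-analysis-set ITT comparison. Bias can go against the bundle (if the prevented courses would have been milder) or in its favour (if more severe), and is absent if they would have been similar. In the illustration it ranges from 3 days against to 3 days in favour, on RRT rates and durations that are assumptions.

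Method 1 escapes the selection if never-RRT patients are given 0 days, which the SAP does not say, but it still rewards early death. Renal recovery has the selection problem only if its denominator is AKI patients, which this SAP does not state. The primary conclusion is unaffected.

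**What to change.** In 3.2 (item 7) and 5.4, make the between-arm comparison for RRT duration the number of days alive and free of RRT through day 30 and through day 90, in all randomized patients. Score death within the window as 0 days and give survivors who never had RRT the full 30 or 90 days. Compare the arms with the center-stratified van Elteren test already planned in 5.4. This matches the free-days endpoints in 3.2 (items 4 and 5).

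Report RRT duration among RRT starters, by both methods, descriptively and without a test between arms, labelled as conditional on starting RRT. State the denominator of renal recovery. If it is AKI patients, treat it in the same descriptive way and let MAKE90 carry the all-randomized comparison of renal outcome. A further recovery composite defined for everyone would be close to the complement of MAKE90 and is not needed.

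The cost is SAP wording and one derived variable per time point, from RRT begin and end dates (4.8.3) and mortality, which the listed endpoints already need. The conditional analyses lose their p-value. The new measure combines death, start of RRT and length of RRT, so it no longer isolates how long a course lasts; the descriptive tables still show that.

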4.1 Baseline Characteristics

- 4.1.1 Number of randomized patients
- 4.1.2 Demographic data (age, sex, BMI, comorbidities, medication)
- 4.1.3 Admission diagnosis and category of admission (elective, emergency)
- 4.1.4 Surgical parameters (nature of surgical procedure, duration of surgical procedure, fluid input and output, intraoperative transfusion)
- 4.1.5 APACHE II
- 4.1.6 Medical history

4.2 Concomitant medication

4.3 SOFA Score

4.4 Hemodynamics

- 4.4.1 MAP
- 4.4.2 HR
- 4.4.3 CVP
- 4.4.4 CI

4.5 Laboratory parameters

- 4.5.1 Glucose
- 4.5.2 Lactate
- 4.5.3 Hemoglobin
- 4.5.4 Na
- 4.5.5 K

4.6 Renal parameters

- 4.6.1 BUN
- 4.6.2 Creatinine
- 4.6.3 GFR
- 4.6.4 Urine output
- 4.6.5 Fluid balance

4.7 Adherence to the KDIGO bundle

4.8 Clinical outcomes (intention-to-treat)

- 4.8.1 AKI (yes/no, severity, diagnosis by, transient/persistent, RRT dependency, type of RRT, RRT days)
- 4.8.2 Mortality
- 4.8.3 Duration of mechanical organ support (Begin and end of RRT, ECMO, and mechanical ventilation)
- 4.8.4 Length of stay (ICU, Hospital)
- 4.8.5 Renal Recovery
- 4.8.6 Need of RRT
- 4.8.7 MAKE

4.9 Adverse events

5 Statistical Methods

Statistical analyses will be performed according to the principles of the ICH guideline E9 'Statistical Principles for Clinical Trials'.

5.1 Randomization and Blinding

Treatment assignment will be accomplished using REDCap and randomization will be performed centrally in a 1:1 proportion, stratified by center. Patients will enter the observation period immediately after randomization.

Neither the patient, nor the study personnel can be blinded in regards to the treatment assignment. The individuals involved in adjudication of endpoints or complications will be blinded to treatment assignment.

Randomization will be checked by comparing demographical and clinical baseline variables between the randomized groups. Differences between treatment groups will be quantified as follows.

1. Normally distributed continuous variables:
Student's two-sample t test, absolute mean difference between groups
2. Non-normally distributed continuous variables:
Wilcoxon two-sample test (t approximation), Hodges-Lehmann estimator of location shift
3. Categorical variables: Absolute difference of percentages, odds ratio
4. Censored variables: Absolute difference of percentages, hazard ratio

5.2 Descriptive summary of study data

All continuous variables will be summarized using the following descriptive statistics: n (non-missing sample size), number of missing values, mean, standard deviation, median, first and third quartile, minimum, maximum.

For categorical variables the frequency and percentages of observed levels will be reported based on the non-missing sample size. All summary tables will be structured with a column for each treatment and will be annotated with the total population size relevant to that table/treatment, including any missing observations.

Censored variables will be summarized using Kaplan Meier estimation.

5.3 Primary statistical analysis: Basic concepts

The primary endpoint occurrence of moderate or severe AKI (stage 2 or 3) within 72 hours after surgery will be evaluated. It is intended to show superiority of the interventional treatment compared to standard care.

The null hypothesis $H_0: AKI_1 = AKI_0$ will be tested at a significance level of 5% against the two-sided alternative $H_1: AKI_1 \neq AKI_0$, where AKI_1 denotes the primary endpoint rate under the interventional treatment and AKI_0 under standard care.

Formally the two-sided test will be decomposed into two one-sided tests of the null hypotheses $H_{0a}: AKI_1 \geq AKI_0$ and $H_{0b}: AKI_1 \leq AKI_0$ against the respective alternatives. The significance level of each of the one-sided tests will be 2.5%.

A group sequential adaptive plan with one interim analysis will be applied. The interim analysis will be performed applying the inverse normal method based on a group sequential plan with O'Brien and Fleming type alpha spending function without futility stop. The interim analysis is planned to be conducted when half of the total number of patients have been recruited (information rate 0.5). The primary statistical analysis will include all randomized patients (full

analysis set) and will be performed according to the intention-to-treat principle (ITT) in order to prevent attrition bias. The randomized groups will be compared with a Cochrane Mantel Haenszel test² with stratification by center. The results of the interim analysis will be compared to the final results in order to find out whether changes in practice may already have occurred during the study period.

The decision bounds of the group sequential adaptive plan for the one-sided tests are shown below.

Information rate	bounds accept H_0	bounds reject H_0	sign.level one-sided	α spent
0.5	-	2.963	0.0015	0.0015
1.0	1.969	1.969	0.0245	0.0250

The primary statistical analysis provides confirmatory statistical evidence.

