5.5 Sample size calculation

Sample size and power calculations are based on a group sequential adaptive plan with one interim analysis and the primary endpoint occurrence of moderate or severe AKI (KDIGO stage 2 or 3) within 72 hours after surgery. The expected AKI rate (\geq stage 2), substantiated by published data of the BigpAK trial, in the control group and the intervention group is 20% and 14%, respectively. The interim analysis will be performed when 309 evaluable patients have been recruited in each treatment group ($2 \times 309 = 618$ patients in total). Using the results of the interim analysis, the sample size of the final analysis will be recalculated (see below). If no sample size adjustment is found to be necessary, the final analysis will be performed when additional 309 evaluable patients have recruited in each treatment group after the interim analysis ($2 \times 309 + 2 \times 309 = 1236$ evaluable patients in total). A number of up to 5% of recruited patients are expected to be lost to follow up and in the worst case have completely non-evaluable data. Therefore, a total number of 1302 patients will be recruited in order to provide a number of 1236 evaluable patients.

The characteristics of the group sequential adaptive plan for the one-sided tests are shown below.

Information rate	bounds accept H_0	bounds reject H_0	sign.level one-sided	α spent	β spent	power achieved	stage n_1	sizes n_2
0.5	-	2.963	0.0015	0.0015	-	0.1647	309.0	309.0
1.0	1.969	1.969	0.0245	0.0250	-	0.8010	309.0	309.0

Calculations were performed using the ADDPLAN software.

5.6 Primary statistical analysis: Details of the interim analysis, sample size adaptation and final analysis

The interim analysis will be performed using data of $n_1 := 2 \times 309 = 618$ evaluable patients (309 patients per treatment group).

If the p-value of the one-sided null hypothesis $H_{0a}: AKI_1 \geq AKI_0$ is $p_a^{interim} \leq 0.0015$, the trial is finished. It will be concluded that the primary endpoint rate under the interventional treatment AKI_1 is lower than under standard care (AKI_0), and that the interventional treatment is superior to standard care.

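### The confirmatory CMH test uses center as its only baseline factor and no adjusted analysis of the primary endpoint is planned: a modest missed efficiency gain, not an error

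*SAP*

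**What the plan says.** SAP 5.3 sets a two-sided 5% test, split into two one-sided tests at 2.5%. It uses the inverse normal method with an O'Brien and Fleming "type alpha spending function without futility stop". On the test itself: "The randomized groups will be compared with a Cochrane Mantel Haenszel test", with center as the stratification factor. This mirrors SAP 5.1, where "randomization will be performed centrally in a 1:1 proportion, stratified by center".

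Baseline information is collected but not used for the primary comparison. SAP 4.1 lists "Demographic data (age, sex, BMI, comorbidities, medication" among others, and also admission category (elective or emergency), surgical parameters and APACHE II. SAP 3.2 has as a secondary endpoint "Change in biomarker values during 12 hours after initial measurement of [TIMP2]*[IGFBP7", so an initial biomarker value exists. The MAKE90 definition in the same section refers to a baseline creatinine. SAP 5.1 compares baseline variables between arms as a check of randomization but attaches no analysis to the result. SAP 6 rules out imputation for effectiveness and safety parameters and does not address baseline covariates.

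**The concern.** Chance imbalance between arms in factors that predict stage 2 or 3 AKI stays in the error of the one confirmatory test. Adjusting for such factors removes part of that variance. The inverse normal method needs only a valid one-sided p-value from each stage, so an adjusted stage-wise test would leave the bounds and the 5.6 sample size rule as they are. Two things are at stake: some power and expected sample size, and the lack of any prespecified adjusted result. If the 5.1 comparison shows an imbalance in an important factor, any adjusted analysis would be post hoc.

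**Working it through.** **Inputs from the SAP.** Event rates: "in the control group and the intervention group is 20% and 14%, respectively" (5.5). Stage 1 has 309 per arm; stage 2 has 309 per arm without adaptation (5.5), or 250 or 400 per arm under the adaptive rule (5.6). The bounds are 2.963 and 1.969 (5.3).

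**Assumptions.** R² is the share of outcome variance the covariates explain beyond center. The SAP gives no value, so a range is shown. α_interim is withheld by design (5.6) and is taken as 0.05, because that value reproduces the 5.7 figures.

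**Formulas.** The pooled rate is (0.20 + 0.14)/2 = 0.17, and 2 × 0.17 × 0.83 = 0.2822. With n per arm in a stage, the expected stage-wise Z is 0.06 / √(0.2822 × (1 − R²) / n). Its standard deviation is √((0.20 × 0.80 + 0.14 × 0.86) / 0.2822) = √(0.2804 / 0.2822) = 0.997. Power is P(Z1 ≥ 2.963) + P(Z1 < 2.963 and (Z1 + Z2)/√2 ≥ 1.969).

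**Step 1: the plan's own figures, R² = 0.**
- Expected Z for stage 1: 0.06 / √(0.2822/309) = 1.985. Without adaptation, the two-stage power is 80.1%, with 16.3% at stage 1. SAP 5.5 states 0.8010 and 0.1647.
- Recruitment: 1236 / 0.95 gives 1302, as stated.
- Adaptive rule: expected Z for stage 2 is 1.786 with 250 per arm and 2.259 with 400 per arm. Power is 81.9%, average N 1146, stage 1 stops 16.3%. SAP 5.7 states 82.1%, 1145.1 and 16.3%.

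The plan reproduces with no covariate adjustment.

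**Step 2: the same calculation with adjustment** (adaptive rule, α_interim = 0.05)

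| R² beyond center | Power, 20% v 14% | Average N | Power, 20% v 15% |
|---|---|---|---|
| 0% | 81.9% | 1146 | 65.9% |
| 2% | 82.6% | 1141 | 66.8% |
| 5% | 83.8% | 1134 | 68.1% |
| 10% | 85.6% | 1120 | 70.4% |

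The table is by numerical integration. Simulation of the same rule agrees to about 0.1 point of power and one patient. At 20% v 15%, SAP 5.7 states 66.0%.

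**Step 3: does the threshold assumption matter?** With α_interim = 0.10, power goes from 80.1% to 80.8% / 82.1% / 83.9% at R² of 2% / 5% / 10%. With 0.15 it goes from 78.9% to 79.6% / 80.7% / 82.8%. The level moves, but the gain stays at about 0.7, 2 and 4 points.

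**Step 4: scale of R².** For one normally distributed risk score in a logistic model at these rates, an AUC of about 0.64 corresponds to 3% variance reduction, 0.69 to 7% and 0.75 to 12%. In the plan without adaptation, R² = 5% gives the same power with 1236 × 0.95 = 1174.2, that is 1175 evaluable patients (61 fewer).

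**The case against.** The strongest reply is that nothing in the plan is stated wrongly. The CMH test uses the factor that stratifies the randomization, needs no outcome model, copes with small centers and cannot lose patients through missing covariates. The power target is met without the change. This stands, and it rules out several stronger readings that a reader might infer.

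- *The trial is underpowered or the test invalid.* Not supported: the stated power reproduces.
- *The collected variables are strongly prognostic.* The SAP gives no prognostic strength for any of them. Section 1.1 describes a biomarker-guided approach in high-risk patients, so the spread of [TIMP2]*[IGFBP7] may be narrowed by selection. Only what the covariates add beyond center counts, since CMH already removes differences in case mix between centers.
- *The unadjusted test saves nothing.* It avoids a covariate rule and reliance on large samples. Stage 1 has about 618 × 0.17 = 105 events and is tested at a one-sided 0.0015, where a model-based variance deserves care. If patients with missing covariates were dropped, 5% missing would cancel an R² of 5% and depart from the full analysis set.
- *All listed variables are usable.* Creatinine and GFR are listed under 4.6, not under baseline, and the SAP does not say when APACHE II is scored. Timing relative to randomization must be confirmed first.

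The reply does not remove the recommendation. These costs can be handled in SAP wording, and the absence of any prespecified adjusted analysis of the primary endpoint remains.

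**Conclusion.** The point holds as a missed efficiency gain. At 20% v 14% the gain is about 0.7 / 1.9 / 3.7 points of power and 5 / 12 / 26 fewer patients on average at R² of 2% / 5% / 10%. The possible totals (618, 1118, 1418) do not change. At the low end this is negligible; at the upper end it is worth having for the cost. The size rests on the assumed R² beyond center, on α_interim = 0.05 for the absolute levels, on a normal approximation, and on all randomized patients staying in the adjusted analysis.

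**What to change.** Decide before any unblinded look.

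1. In 5.3, define the stage-wise primary statistic as either a randomization-based covariance-adjusted CMH stratified by center, or a standardized risk difference from a logistic model with center included, small centers pooled by a stated rule, and robust variance. Both keep the comparison of AKI_1 with AKI_0.
2. Name a short list of covariates, for example age, elective or emergency admission, log initial [TIMP2]*[IGFBP7] and baseline creatinine. Include each only once it is confirmed to be measured before randomization.
3. State a rule for missing covariates, such as a missing indicator or a single fill-in blind to arm, so that every patient who would enter the CMH test also enters the adjusted one.
4. Compute the statistic separately on each stage's patients and feed the one-sided p-values into the same inverse normal combination. The bounds, α_interim and the n2 rule stay as they are.
5. Keep the unadjusted CMH as sensitivity analysis.

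The cost is SAP wording, one extra model per stage, a covariate rule and reliance on large-sample validity at the 0.0015 interim level, which a short simulation can check. No new data are needed. If the sponsor keeps CMH as primary, or the interim has already been unblinded, the adjusted analysis can be named as supportive. That gives a prespecified robustness check but recovers no confirmatory power.
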